## 8.5 Pharmacokinetic Statistical Methodology

All tables, figures, and listings (TFLs), when appropriate, will be stratified by cohort.

### 8.5.1 Summary Statistics

Summary statistics of the individual concentration data and derived parameters will be calculated with SAS for the PK population. Summary statistics will be calculated for concentration at each individual time point and for all PK parameters.

Concentration data will be listed by subject number and summarized by treatment using the following statistics: number of observations (N), mean, SD, min, median, max, and coefficient of variation (CV%). The PK parameters will be summarized using these same statistics, as well as geometric mean and geometric CV%.

### 8.5.2 Statistical Analysis

Natural log-transformed PK parameters (Cmax, AUC0-inf, and AUC0-T) will be assessed statistically for proportionality. Proportionality analysis will be done using a power model. The power model is defined as:

$$\ln(\text{PK parameter}) = \alpha + \beta \cdot \ln(\text{Dose}) + \varepsilon$$

where  $\alpha$  is the intercept,  $\beta$  is the slope and  $\varepsilon$  is the error term. A linear model with ln-transformed dose as a continuous effect will be fitted. A point estimate and a 90% confidence interval will be derived for the slope ( $\beta$ ).

The mixed effect statistical model using PROC MIXED procedure in SAS will be used for dose proportionality assessment. If the mixed model failed to converge, a PROC GLM will be used. If there are less than 3 subjects for valid PK parameters (Cmax, AUC0-T and AUC0-∞) or less than 3 subjects for one of valid PK parameters per cohort, this cohort or particular PK parameter within this cohort would be considered as exclusion of dose proportionality assessment.

The parameter can be considered to be dose-proportional if the 90% CIs for the slope coefficient that include 1 will suggest evidence of dose proportionality.

Dose proportionality may be assessed within different dose ranges if deemed appropriate with at least three doses.

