### 3 STUDY DESIGN

#### 3.1 General Description

This single center, single-dose, randomized, adaptive, double-blind, placebo-controlled study will consist of 5 SAD cohorts. A total of 40 healthy, male and female nondependent, recreational polydrug users with opioid experience (8 subjects in each of the 5 cohorts) will be included.

Subjects will only participate in 1 cohort. The planned dose levels by cohort are presented in [Table 3-1](#).

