## 5 DATA HANDLING AND PRESENTATION

All safety and statistical outputs will be generated using SAS software, version 9.4 or higher. The PK outputs will be generated using the same version of SAS.

All programs used to generate statistical analyses will be validated according to Altasciences' Standard Operating Procedures (SOPs).

The analyses described in this plan are considered a priori, in that they have been defined prior to database lock and/or prior to breaking the blind. Any analyses performed subsequent to database lock and/or breaking the blind will be considered post hoc and exploratory, and will be identified in the Clinical Study Report (CSR).

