### 8.4 Non-Compartmental Analysis

The following configuration for the NCA analysis (with Phoenix® WinNonlin® version 8.0, or higher) will be used:

- Data: Serial Sampled Data
- Model/Dose options Type: Plasma (200 -202) / Extravascular
- AUC Calculation Method: Linear-Up/Log-Down
- Lambda Z ( $\lambda_Z$ ) calculation: Best fit method for  $\lambda_Z$  Linear-Log regression

Reasons for excluding PK parameters will include the following:

- AUC: AUC parameters will not be estimated if less than 3 consecutive measurable concentrations are observed
- PK parameters requiring  $\lambda_Z$  estimation (eg,  $AUC_{0-\infty}$  and  $T_{\text{half}}$ ) will be set to Not Reported (NR) in the tables and listings if they meet one of the following:
  - $R^2 < 0.8$
  - The terminal half-life is higher than 2 times the time interval over which  $\lambda_Z$  is estimated (ie.  $T_{\text{half}} >$  twice the time interval difference between  $\lambda_Z$  Upper and  $\lambda_Z$  Lower).

The PK parameters for mitragynine, 7-hydroxy-mitragynine, paynantheine, speciogynine, and speciociliatine are defined in [Table 8-1](#).

**Table 8-1 Pharmacokinetic Parameters of Mitragynine, 7-Hydroxy-Mitragynine, Paynantheine, Speciogynine, and Speciociliatine in Plasma**

Parameter	Definition
$C_{\text{max}}$	Maximum observed concentration
$C_{\text{max}}/D$	Dose-normalized $C_{\text{max}}$ calculated at $C_{\text{max}} / \text{Dose}$
$T_{\text{max}}$	Time of maximum observed concentration; if it occurs at more than 1 timepoint, $T_{\text{max}}$ is defined as the first timepoint with this value
$AUC_{0-T}$	Area under the concentration time curve from time zero to the time of last quantifiable concentration ( $T_{\text{last}}$ )
$AUC_{0-T}/D$	Dose-normalized $AUC_{0-T}$ calculated as $AUC_{0-T} / \text{Dose}$
$AUC_{0-\infty}$	Area under the concentration time curve extrapolated to infinity, calculated as $AUC_{0-T} + C_{\text{last}}/\lambda_Z$ , where $C_{\text{last}}$ is the last quantifiable concentration at time $T_{\text{last}}$
$AUC_{0-\infty}/D$	Dose-normalized $AUC_{0-\infty}$ calculated as $AUC_{0-\infty} / \text{Dose}$
AUC%Extrap	Extrapolated area (ie, percentage of $AUC_{0-\infty}$ due to extrapolation from $T_{\text{last}}$ to infinity: $AUC_{0-\infty} - AUC_{0-T} / AUC_{0-\infty} * 100$ )
$\lambda_Z$	Apparent elimination rate constant, estimated by linear regression of the terminal linear portion of the log concentration versus time curve

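### The SAP takes a 90% confidence interval for the power-model slope that includes 1 as evidence of dose proportionality, so an imprecise estimate can earn a positive conclusion

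*SAP*

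**What the plan says.** SAP 8.5.2 uses the power model ln(PK parameter) = α + β·ln(Dose) + ε for Cmax, AUC0-T and AUC0-∞. On the fit it says "A linear model with ln-transformed dose as a continuous effect will be fitted", and on the output "A point estimate and a 90% confidence interval will be derived for the slope". The decision rule is that a parameter can be regarded as dose-proportional "if the 90% CIs for the slope coefficient that include 1 will suggest evidence of dose proportionality".

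Three other provisions bear on how precise that interval will be:

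- A cohort, or one parameter within it, is left out only below a floor: "If there are less than 3 subjects for valid PK parameters" (SAP 8.5.2). Three valid values are therefore enough to stay in.
- Parameters that depend on the terminal slope "will be set to Not Reported (NR) in the tables and listings if they meet one of the following", the criteria being a poor fit or too short an estimation interval (SAP 8.4). Among the three tested parameters this affects AUC0-∞.
- Narrower fits are permitted: "Dose proportionality may be assessed within different dose ranges if deemed appropriate with at least three doses" (SAP 8.5.2). No sub-range is named.

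Protocol 8.4 gives no proportionality criterion and leaves PK statistics to the SAP. Protocol 8.7 and SAP 3.5 state that no formal sample size analysis was done.

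**The concern.** A 90% interval that includes 1 is the same event as failing to reject β = 1 in a two-sided test at the 0.10 level. That can happen because β is close to 1 or because the data are too few or too variable to tell. The rule does not separate the two cases and gives both the favourable label. It also works the wrong way round at the other extreme: with very precise data, a trivial departure would lose the label.

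The rule covers 15 parameter-by-analyte combinations (3 parameters × 5 alkaloids), so the study report could state proportionality for several alkaloids on uninformative data. Protocol 1.3 names PK among the things this study examines to find a dose range for a later human abuse potential study. A reader who takes a proportionality statement at face value could scale exposure linearly across doses when the data do not support it.

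**Working it through.** **No figure to reproduce.** The documents state no CV, margin, power or sample size for this analysis. What can be calculated is how the rule behaves under the planned design.

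**Inputs from the documents**
- Sample doses 1, 2, 4, 6 and 8 g (SAP Table 3-1); these may change during the study.
- Six active subjects per cohort (SAP 3.4); placebo subjects are outside the PK population (SAP 4.3). N = 5 × 6 = 30.
- One dose per subject: "Subjects will only participate in 1 cohort" (SAP 3.1). The mixed model therefore reduces to ordinary regression.
- 90% interval; floor of three valid values per cohort; sub-ranges of at least three doses (SAP 8.5.2).

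**Assumption:** between-subject CV of 20% to 80%.

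**Formulas**
- σ = √ln(1 + CV²)
- Sxx = Σ(ln dose − mean ln dose)², summed over subjects
- SE(β) = σ/√Sxx; interval half-width = t(0.95, N−2) × SE
- P(interval includes 1) = P(|T| < t(0.95, N−2)), with T noncentral t on N−2 degrees of freedom and noncentrality (β − 1)√Sxx/σ
- Dose-normalised exposure, highest versus lowest dose = r^(β−1), where r is the dose ratio

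**One case in full: all five cohorts, CV 50%, β = 0.8**
- The log doses are 0, 0.693, 1.386, 1.792 and 2.079, with mean 1.190. Their squared deviations sum to 2.855, so Sxx = 6 × 2.855 = 17.13.
- σ = √ln(1.25) = 0.472. SE = 0.472/√17.13 = 0.114.
- t(0.95, 28) = 1.701. Half-width = 1.701 × 0.114 = 0.194.
- Noncentrality = −0.2 × 4.139/0.472 = −1.75.
- P(interval includes 1) = 47.4%.
- True exposure ratio = 8^(−0.2) = 0.66.

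**Probability that the rule gives the proportional label**

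| Design | True β (exposure ratio) | CV 20% | CV 30% | CV 50% | CV 80% |
|---|---|---|---|---|---|
| 1–8 g, 6 per dose (N = 30, Sxx 17.13) | 1.0 (1.00) | 90% | 90% | 90% | 90% |
| same | 0.8 (0.66) | 0.8% | 13% | 47% | 69% |
| same | 0.7 (0.54) | 0.0% | 0.7% | 18% | 47% |
| 1–8 g, 5 per dose (N = 25, Sxx 14.27) | 0.8 (0.66) | 2% | 20% | 54% | 72% |
| 1–8 g, 3 per dose (N = 15, Sxx 8.56) | 0.8 (0.66) | 12% | 40% | 68% | 80% |
| 1, 2, 4 g, 6 per dose (N = 18, Sxx 5.77) | 0.8 (4^(−0.2) = 0.76) | 25% | 53% | 74% | 83% |
| 4, 6, 8 g, 6 per dose (N = 18, Sxx 1.455) | 0.5 (2^(−0.5) = 0.71) | 10% | 37% | 66% | 79% |

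The 1, 2, 4 g row is what remains if escalation ends after the third sample dose.

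**What an interval centred exactly on 1 leaves open (N = 30).** Half-widths of 0.121, 0.194 and 0.289 at CV 30%, 50% and 80% give 8^(±half-width): dose-normalised exposure at 8 g between 0.78 and 1.29, 0.67 and 1.50, or 0.55 and 1.82 times that at 1 g.

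**The alternative rule, for comparison.** Require the whole interval to lie inside 1 ± ln(m)/ln(r), where m is a margin on the exposure ratio. With m = 1.25 (an assumption) and r = 8, this is 1 ± 0.2231/2.0794, or 0.893 to 1.107. At true β = 1 and N = 30 the chance of meeting it is 41.5% at CV 20%, 2.2% at CV 30% and about 0 at CV 50%. With m = 2 (also an assumption) the limits are 0.667 to 1.333 and the chance is 99.7% at CV 30% and 77.2% at CV 50%. Here less precision makes the claim harder.

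**The case against.** Several objections have force.

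- *The perverse behaviour is not universal.* At β exactly 1 the label is given 90% of the time whatever the precision. This is correct. The argument concerns true slopes other than 1, which are the ones a proportionality check is meant to catch.
- *The size depends on assumed CVs.* It does. At CV 20% with the full design the rule rarely misleads for β = 0.8 (0.8%). Nothing in the documents shows that the CV will be that low.
- *Three per cohort is an extreme.* It needs every cohort to lose half its active subjects for the same parameter, and the terminal-slope exclusion reaches only AUC0-∞, 5 of the 15 combinations. Losing one subject per cohort is a milder case and raises 47% only to 54% at CV 50%. The full design already shows the problem.
- *The dose range may widen.* The SAP lets the top dose exceed 8 g. An illustrative set of 1, 2, 4, 8 and 12 g gives 5%, 35% and 61% at CV 30%, 50% and 80% for β = 0.8, which is better but still not negligible. Early termination of escalation works in the opposite direction.
- *Late sub-range fits are already labelled.* SAP 5 says "Any analyses performed subsequent to database lock and/or breaking the blind will be considered post hoc and exploratory". This covers sub-ranges chosen late. It does not cover ones chosen before lock, and it leaves the full-range rule as it is.
- *The analysis is minor and openly reported.* Proportionality is not itself an objective or endpoint, the wording is cautious, and the slope, its interval and dose-normalised summaries are all planned. A careful reader could see a wide interval. This limits the consequence, but the SAP still prescribes the wrong sentence to write beside that interval.
- *An equivalence rule would almost never be met.* Under the 1.25 margin that is largely so. It shows that the design usually cannot establish proportionality that tightly, which is a reason not to make proportionality the default reading.

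**Conclusion.** The concern holds. SAP 8.5.2 treats non-rejection as evidence, and no margin or precision condition elsewhere corrects it. With the sample doses and six active subjects each, a one-third loss of dose-normalised exposure across the range (β = 0.8) would be labelled proportional about 13% of the time at CV 30%, 47% at CV 50% and 69% at CV 80%, and under 1% at CV 20%. The logic of the error does not depend on the CV, but these probabilities do. They also assume log-normal errors with constant variance and the sample doses as listed.

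The change should be made, but the reach is limited. The primary safety objective is unaffected, and so is escalation, which rests on safety and PD data. The estimates themselves are sound; the fault is in the conclusion drawn from them.

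**What to change.** Replace the decision sentence in SAP 8.5.2 with the following.

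1. If the 90% interval for β excludes 1, report *departure from dose proportionality detected*. If it includes 1, report *no departure detected; proportionality not established*.
2. For every parameter and analyte, report β, its 90% interval, and r^(β−1) with the interval obtained by transforming the limits for β. Take r from the highest and lowest doses actually given and analysed.
3. State *dose-proportional* only if the whole interval lies inside limits fixed before unblinding, for example 1 ± ln(m)/ln(r) with m chosen by the sponsor. If an interval excludes 1 but lies inside the limits, report both facts. If no margin can be justified, omit the positive claim and keep items 1 and 2.
4. Name any dose sub-ranges before unblinding, or label them exploratory and say that they do not replace the full-range result.

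**Cost.** A few sentences of SAP text and one derived line in the PK table; no new data or subjects. Detection of real departures is unchanged, because an interval excluding 1 is still reported as one: at β = 0.8 and N = 30 the chance is 87%, 53% and 31% at CV 30%, 50% and 80%. The drawback is that under a tight margin such as 1.25 nearly every parameter will read *not established* at CV 30% or more, and the sponsor should expect that.

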## 9 PHARMACODYNAMIC ANALYSIS

Unless otherwise specified, all available PD data and analysis results will be presented for the Completer population.

The PD measures at each time point will be summarized by treatment using descriptive statistics and presented graphically. Derived endpoints will be summarized by treatment and paired difference using descriptive statistics.

Descriptive statistics will include n, mean, standard error (SE), minimum, first quartile (Q1), median, third quartile (Q3) and maximum for all PD values and endpoints other than  $TE_{max}$  and  $TE_{min}$ . For  $TE_{max}$  and  $TE_{min}$ , minimum, Q1, median, Q3 and maximum will be presented.

Derivations for PD endpoints will be calculated as described below:

PD Endpoints	Definition
$E_{min}$	Minimum observed post-dose effect
$E_{max}$	Maximum observed post-dose effect
$TE_{min}$	Time of minimum observed post-dose effect
$TE_{max}$	Time of maximum observed post-dose effect
TA_AUE 	Time-averaged area under the effect-time curve (pre-dose - post-dose)
TA_AOE 	Time-averaged area over the effect-time curve (pre-dose - post-dose)

For time-averaged area over the effect-time-curve and area under the effect-time-curve (TA-AUE and TA\_AOE), will be calculated as the area over(or under) the curve relative to the baseline value divided by the time from time 0 to the X hour time point. TA\_AOE will be calculated using the linear trapezoidal rule applied to non-missing data. TA\_AOE will not be calculated if the first or last scheduled time point are missing. Assessments performed outside the assessment windows may be excluded from by-time point summary statistics; this will be determined prior to unblinding.

Derived Variable	Variables Used	Calculation	Comment
TA_AUE and TA_AOE	PD effect score $E_i$ at actual elapsed times $t_i$ over one inter-dosing interval.	$AUE_i = (t_i - t_{i-1}) \frac{(E_i + E_{i-1})}{2}$ 
then
 $AUE = \sum_{i=1}^n AUE_i$ 
summation over all time intervals from time 0 (or the first time point if the PD measure is not collected predose) to the X-hour (ie, last) time point.
 
TA_AUE is calculated as the AUE divided by the time from time 0 (or the first time point if the PD measure is not collected predose) to the X-hour time point.
 
TA_AOE will be calculated using the same procedure and TA_AUE with the exception that increases compared to baseline are expected so areas are expected to fall over baseline instead if below baseline.
	Trapezoidal rule used to the 2 consecutive non-missing data points Missing data are ignored. The actual elapsed time $t_0$ for the predose value is set to 0.

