6.3. Pharmacodynamic Assessments

Pharmacodynamic assessments will be performed throughout the study as outlined in [Table 6-1](#).

Prior to completing the computerized PD measures, all subjects will undergo a scripted training and practice regimen. Eligible subjects who appear to have difficulty differentiating between bipolar and unipolar visual analog scales (VAS) (e.g., making errors such as selecting a score of 50 to indicate the absence of a drug-effect on a unipolar scale) or difficulty distinguishing between "at this moment" and "next-day" measures will undergo additional training on the difference between the scale types. Additional training sessions will be documented in source files.

Testing conditions for PD assessments should remain as consistent as possible. Subjects will be monitored carefully to ensure that they are completing the PD assessments appropriately; all reasonable attempts should be made to rouse subjects who fall asleep during testing cycles. If subjects cannot complete the PD assessments in a timely manner prior to the next required procedure or timepoint due to an AE, testing will be aborted.

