### **4.4 Completer Population**

All subjects in the Safety population who complete the dose level or placebo in their cohort, and have sufficient data for evaluation of the primary endpoint (based on a blinded review of data prior to database lock) will be included in the Completer population. Subjects who do not have at least 1 observation within 2 hours of  $T_{max}$  for Drug Liking VAS will be excluded from the Completer population.

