**Table 9-3. Subjective Measures Schedule**

Category	Evaluations	Timepoints
Drug-specific VAS	Drug Liking, Good Drug Effects, Bad Drug Effects, and Any Drug Effects	0.25, 0.5, 1, 1.5, 2, 2.5, 3, 4, 6, 8, 10, 12, and 24 hours postdose
	Overall Drug Liking and Take Drug Again	12 and 24 hours postdose
Other VAS	High, Feeling Drunk, Relaxation/Agitation, Drowsiness/Alertness, and Bowdle VAS	Predose and 0.25, 0.5, 1, 1.5, 2, 2.5, 3, 4, 6, 8, 10, 12, and 24 hours postdose
	Drug Similarity	12 hour postdose
ARCI Scales	MBG, A, BG, PCAG, and LSD	Predose and 0.25, 0.5, 1, 1.5, 2, 2.5, 3, 4, 6, 8, 10, 12, and 24 hours postdose

Abbreviations: A = amphetamine; BG = Benzedrine Group; LSD = Lysergic Acid Diethylamide; MBG = Morphine-Benedrine Group; PCAG = Pentobarbital–Chlorpromazine–Alcohol Group; VAS = visual analog scale.

Windows for timed subjective measurements are presented in [Table 9-4](#).

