### 9.3 Analysis of Pharmacodynamics Measures

The primary PD endpoint of this study is the maximum (peak) effect (Emax) over 24 hours for Drug Liking (“at this moment”), assessed on a bipolar (0 to 100 points) visual analog scale (VAS). This endpoint will be summarized with descriptive statistics. Placebo will be pooled across all cohorts.

$E_{max}$  as well as  $T_{max}$  and TA\_AUE of key secondary PD endpoints, Overall Drug Liking, Take Drug Again, and High VAS will be summarized similarly by treatment for the Completer population using descriptive statistics. All PD measures at each time point will be summarized by treatment using descriptive statistics and presented graphically. Derived endpoints will be summarized by treatment and paired difference using descriptive statistics.

A mixed-effects model will be used to compare PD endpoints between Kratom dose levels and placebo for all primary and secondary PD endpoints other than the 12-hour postdose results from Drug Similarity VAS and  $TE_{max}$  and  $TE_{min}$  endpoints. The model will include dose level as a fixed effect and the baseline score as a covariate [where applicable]. P-values for key components of variance, least-square means (LSmeans), and 95% CI for contrasts will be output for each pairwise comparison for Kratom dose levels versus placebo.

For each PD endpoint, the following comparison will be made:

- Kratom 1 g vs. Placebo
- Kratom 2 g vs. Placebo
- Kratom 4 g vs. Placebo
- Kratom 6 g vs. Placebo
- Kratom 8 g vs. Placebo

The Hodges-Lehmann estimate of the location shift, the asymptotic confidence limits, and the asymptotic standard error estimate will be used to estimate the 95% CIs of  $TE_{max}$  and  $TE_{min}$  secondary endpoints between the Kratom dose levels and placebo. The asymptotic standard error estimate is based on the length of the CIs. Rank sums and p-values from the Wilcoxon Rank Sum test will also be output.

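### All PD endpoints share one Completer set fixed after dosing, so a subject with valid 12/24 h ratings or pupil data may be dropped from those endpoints because of missing Drug Liking data

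*SAP*

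**What the plan says.** SAP section 9 states: "Unless otherwise specified, all available PD data and analysis results will be presented for the Completer population". Protocol 8.5 has the same rule. SAP 9.3 repeats it for the key secondary endpoints, which "will be summarized similarly by treatment for the Completer population using descriptive statistics". SAP 9.1 names no other set for pupillometry. The Randomized and Safety populations are defined but carry no PD analysis, and no PD sensitivity analysis is planned.

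SAP 4.4 (and Protocol 8.1.4) sets three conditions for the Completer population:

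- Dose completion: "All subjects in the Safety population who complete the dose level or placebo in their cohort".
- Sufficient data: subjects must "have sufficient data for evaluation of the primary endpoint (based on a blinded review of data prior to database lock").
- A rating near the peak: "Subjects who do not have at least 1 observation within 2 hours of" Tmax "for Drug Liking VAS will be excluded from the Completer population".

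In SAP Table 9-3 the Drug Liking schedule has 13 post-dose times, ending "12, and 24 hours postdose". Overall Drug Liking and Take Drug Again are asked at 12 h and 24 h only. Pupillometry has its own schedule and is done immediately before the other PD measures (SAP 9.1). Protocol 6.3 adds that if a subject cannot finish the PD assessments before the next "procedure or timepoint due to an AE, testing will be aborted".

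**The concern.** Each subject takes one dose in one cohort, so no within-subject comparison requires a completer set. All three conditions are known only after dosing, and the two data conditions appear to concern one scale. Neither a 12 h or 24 h Take Drug Again score nor a pupil diameter needs a Drug Liking rating near the peak, yet a subject who fails the Drug Liking conditions leaves those endpoints too.

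The loss is plausibly related to dose. Testing is aborted for adverse events. The protocol gives vomiting as the reason for fed dosing (1.1), describes strong sedation above 7 to 8 g (1.3) and expects that some subjects may have to be roused for testing (6.3). If subjects with a poor high-dose experience are removed from the retrospective scales, mean Overall Drug Liking and Take Drug Again at those doses are raised. The study is meant to inform the dose range of a later abuse-potential study (Protocol 1.3), so the shape of that dose-response matters.

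**Working it through.** **Plan's own figure.** 5 cohorts × (6 + 2) = 40, that is 30 active and 10 placebo (SAP 3.1, 3.4), which agrees with the stated total. Placebo is pooled (SAP 9.3), so each contrast is 6 against 10. SAP 3.5 gives no power, SD or dropout rate to reproduce.

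**When does the 2-hour rule exclude someone?** SAP 4.4 does not say which Tmax it means.

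- *Plasma Tmax.* A subject fails only by missing every scheduled Drug Liking rating within 2 h of it. The number of nominal times in that window is:

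| Tmax (h) | 1 | 1.5 | 2 | 2.5 | 3 | 4 | 6, 8 or 10 | 12 |
|---|---|---|---|---|---|---|---|---|
| Ratings in window | 7 | 7 | 8 | 7 | 6 | 5 | 3 | 2 |

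  Example: with Tmax at 2 h, a subject with no subjective ratings through 4 h who resumes at 6 h fails, yet has both ratings of Overall Drug Liking and Take Drug Again. Placebo-only subjects are outside the PK population (SAP 4.3), so this reading gives them no individual Tmax.
- *The subject's own time of peak Drug Liking.* SAP 9.3 also writes Tmax for PD endpoints. Anyone with any Drug Liking score then passes automatically. Drug Liking is itself rated at 12 h and 24 h, so a subject with those ratings is not removed by this rule. Exclusion would rest on dose completion or on the undefined sufficiency judgment.

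The sufficiency condition refers to the primary endpoint. That is safety in SAP Table 2-1, while SAP 9.3 calls Drug Liking Emax the primary PD endpoint. The second reading is the more natural one, but the text does not settle it.

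**Shift in a dose-group mean.** Suppose k of 6 are excluded and score g points below those retained (mean M). The all-dosed mean is [(6 − k)M + k(M − g)]/6 = M − gk/6, so the Completer mean is too high by gk/6. The values of g are assumptions; the documents give none.

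| g (points) | k = 1 | k = 2 |
|---|---|---|
| 10 | 1.7 | 3.3 |
| 25 | 4.2 | 8.3 |
| 50 | 8.3 | 16.7 |

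**How often.** For an assumed exclusion probability p per subject, P(at least 1 of 6) = 1 − (1 − p)^6, which is 26% at p = 5% and 47% at p = 10%. P(at least 2 of 6) = 1 − (1 − p)^6 − 6p(1 − p)^5, which is 3.3% and 11.4%.

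**Precision.** SE = SD × √(1/n active + 1/n placebo), with common variance, no baseline covariate (the 12/24 h scales have none) and t on N − 6 df:

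| Active vs placebo | SE/SD | Change | df | 95% CI half-width/SD |
|---|---|---|---|---|
| 6 vs 10 | 0.516 | – | 34 | 1.05 |
| 5 vs 10 | 0.548 | +6.1% | 33 | 1.11 |
| 4 vs 10 | 0.592 | +14.6% | 32 | 1.21 |

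**Comparison within the SAP.** SAP 4.3 lets a subject with missing samples stay in for PK parameters judged unaffected. PD has no equivalent.

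**The case against.** The strongest reply is that the harm is unlikely and contained. Sufficiency is judged blind before database lock, which rules out selection by known treatment. Dosing is a single supervised administration with 48 h of confinement, and staff try to rouse sleepy subjects. Under the plasma reading a subject must miss 5 to 8 scheduled ratings for a Tmax of 1 to 4 h; under the own-peak reading the 2-hour rule removes nobody who has a score. PD is secondary in a pilot with no formal sample size, and primary safety uses the Safety population. SAP 6.1 reports numbers in each population by treatment, so exclusions will be visible. All of this stands, and it limits the size of the point. However, blinding does not correct missingness that itself depends on dose.

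Some stronger inferences are tempting but not supported:

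- *A single Drug Liking criterion automatically removes such a subject.* There are three conditions, and the outcome depends on the meaning of Tmax and on an undefined judgment.
- *Bad Effects is understated.* It is rated at the same times as Drug Liking, so a subject aborted around the peak normally lacks peak Bad Effects too; adding only late scores could lower that mean.
- *Every PD endpoint should move to all dosed subjects with any post-dose value.* Emax is the largest observed post-dose score (SAP 9), so a lone 24 h rating would stand as the peak for Drug Liking, High, Good, Bad or Any Effects.
- *The 12/24 h argument covers every key secondary.* High VAS is rated through the time course, so it does not.
- *Exclusions are what separate the contrast from the randomised groups.* Placebo is already pooled across cohorts: 8 of the 10 placebo subjects in each contrast were randomised in other cohorts.

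**Conclusion.** The point holds in a limited form. Every PD endpoint is confined to one set, fixed after dosing, whose data conditions appear to centre on Drug Liking. That restriction has no rationale for Overall Drug Liking, Take Drug Again or pupillometry, and it may discard valid data there. Exclusions should be few. One lost active subject is 1/6 of a dose group, moves its mean by about 4 points if the excluded subject scores 25 points below those retained, and widens the standard error by about 6%. The gap is assumed (10 to 50 points gives 1.7 to 8.3), and a bias arises only if exclusion is related to the outcome. The larger shifts need two losses in one group, which is improbable at the assumed rates. The primary safety analysis is unaffected. This is a cheap improvement worth making before unblinding.

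**What to change.** In SAP 4.4, 9 and 9.3, and in Protocol 8.1.4 and 8.5, decide PD inclusion endpoint by endpoint, following the principle of SAP 4.3:

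- **Overall Drug Liking and Take Drug Again:** all dosed subjects with a 12 h or 24 h score, without the Drug Liking criterion.
- **Pupillometry:** all dosed subjects with a baseline and adequate post-dose pupil data, without the Drug Liking criterion. Define adequate in advance, because a partial profile can miss the maximum constriction.
- **Time-course Emax scales (Drug Liking, High, Good, Bad and Any Effects):** keep the Completer analysis and add an all-dosed sensitivity analysis on available data.
- **Definitions:** before unblinding, state which Tmax the 2-hour rule uses, how it applies to placebo subjects, which endpoint the sufficiency condition means, and what counts as sufficient.

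The cost is document wording and one extra run of the same tables; no trial procedure changes. The small downside is that partial profiles in the sensitivity analysis can understate a peak, which is why Completer stays the main set for those scales.
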